The primary outcome measure is progression free survival (PFS) in patients with MPNST at the recommended dose determined from the Phase 1 study, Dose level 3 (1000mg of Turalio® orally total daily in combination with 2mg of Sirolimus orally once daily). Progression free survival is defined as the time from the start of treatment until disease progression or death from any cause. Patients who have not progressed will be censored at the date of their last follow-up. Patients will be evaluated weekly for the first three weeks, at least every other week during the first two cycles and then at the beginning of every subsequent cycle. Tumor response will be assessed by CT scans performed every six weeks for the first six months, every eight weeks for the following six months, and then every 12 weeks thereafter using Response Evaluation Criteria in Solid Tumors (RECIST) 1.1. Assuming a median PFS of 6 weeks in patient treated with the standard of care (23), with a sample size of 25, we have 90% power to detect a difference of 12 weeks in median PFS (6 weeks versus 18 weeks) given a 2-sided test with an alpha of 0.05.

Patients will be required to obtain research-specific biopsies as follows:

- 1) Baseline biopsy of a target lesion
- 2) Repeat biopsy during last week of cycle 1 for pharmacodynamic analysis
- 3) Optional biopsies at time of progression

All biopsies will attempt to obtain 4-5 cores. Two of the cores will be processed for formalin fixation and 2-3 will be frozen in liquid nitrogen for exploratory analyses.

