#### **7.4 Duration of Follow Up**

Patients will be followed after completion or removal from study or until death, whichever occurs first. Patients removed from study for unacceptable adverse events will be followed until resolution or stabilization of the adverse event. Thereafter, patients will be contacted by phone every 3 months during year 1 and every 6 months thereafter to obtain information about subsequent treatment(s) and survival status.

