#### **7.5 Criteria for Removal from Study**

The reasons a patient may discontinue or be withdrawn from the study include, but are not limited to, adverse event, clinically significant disease progression, patient request, investigator decision, protocol violation, patient noncompliance, and study termination by the Sponsor or institutional review board (IRB)/independent ethics committee (IEC).

When a patient discontinues or is withdrawn, the investigator will notify the Sponsor and should perform the procedures indicated in the End of Study column in the Schedule of Events within 28 days after discontinuation of study drug and before initiation of any new anti-cancer therapy. Follow-up information will be obtained for patients who discontinue their participation in or are withdrawn from the study.

Patients withdrawn from the study for reasons other than toxicity or clinically significant disease progression (e.g., protocol violation or noncompliance) may be replaced at the discretion of the medical monitor and the investigator. Study drug administration may be discontinued for an adverse event or at the discretion of the investigator.

The consequence of withdrawal of all consent by a patient will be that no new information will be collected from that patient and added to the existing data or any database. However, every effort will be made to follow all patients for safety.

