## **8.2 Phase 2 Dose Modification**

Patients may have dose modifications at any time. Patients may have either drug held for any reason for up to 21 days before discontinuing study treatment. Refer to Tables 10 – 14 below for specific dose modification instructions.

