#### Response classification for Patients with Measurable Disease (e.g., Target Disease)

| Target Lesions | Non-Target Lesions          | New Lesions | Overall Response | Best Response when Confirmation is Required* |
|----------------|-----------------------------|-------------|------------------|--|
| CR             | CR                          | No          | CR               | 8 weeks                                      |
| CR             | Non-CR/Non-PD               | No          | PR               | 8 weeks                                      |
| CR             | Not evaluated               | No          | PR               |  |
| PR             | Non-CR/Non-PD/not evaluated | No          | PR               |  |
| SD             | Non-CR/Non-PD/not evaluated | No          | SD               | 8 weeks                                      |
| PD             | Any                         | Yes or No   | PD               | no prior SD, PR or CR                        |
| Any            | PD**                        | Yes or No   | PD               |  |
| Any            | Any                         | Yes         | PD               |  |

\* See RECIST 1.1 manuscript for further details on what is evidence of a new lesion.

\*\* In exceptional circumstances, unequivocal progression in non-target lesions may be accepted as disease progression.

Note: Patients with a global deterioration of health status requiring discontinuation of treatment without objective evidence of disease progression at that time should be reported as “symptomatic deterioration.” Every effort should be made to document the objective progression even after discontinuation of treatment.

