## **11.6 Progression-Free Survival**

PFS is defined as the duration of time from start of treatment to time of progression or death, whichever occurs first.

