### **13.3 Analysis of Primary and Secondary Endpoints and Evaluation of Tissue**

#### **13.3.1 Primary Analysis**

**Phase I:** The MTD will be estimated using the Continual Reassessment Method. The proportion of DLT at each dose level will be reported along with the final estimates of the probability of DLT based on the TTE-CRM.

**Phase II:** Progression free survival will be estimated using the Kaplan Meier method. Median PFS and 95% confidence intervals will be reported.

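### PFS is censored at an undefined 'last follow-up' that need not be a tumour assessment, so unscanned months after stopping treatment can count as progression-free

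*Combined protocol and SAP*

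**What the plan says.** Section 4.1 (Phase 2) defines the endpoint: "Progression free survival is defined as the time from the start of treatment until disease progression or death from any cause". The next sentence is the censoring rule: "Patients who have not progressed will be censored at the date of their last follow-up". What counts as follow-up is not defined.

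Section 11.6 restates the endpoint without a censoring rule: "PFS is defined as the duration of time from start of treatment to time of progression or death, whichever occurs first". Section 13.3.1 says only "Progression free survival will be estimated using the Kaplan Meier method", with a median and 95% confidence interval.

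Section 7.4, on duration of follow-up, describes phone contact after patients leave: every 3 months in year 1 and every 6 months after that, covering later treatment and survival. It mentions no tumour assessment.

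Two passages soften this. A note in section 11.4.3, about symptomatic deterioration, says "Every effort should be made to document the objective progression even after discontinuation of treatment". Section 7.5 says the investigator "should perform the procedures indicated in the End of Study column in the Schedule of Events within 28 days after discontinuation of study drug". The Schedule of Events is not in the supplied text, so an End of Study scan cannot be ruled out.

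**The concern.** Progression is found by imaging. A censoring date later than the last scan asserts that the patient was progression-free when nobody had looked. The protocol provides several ways to leave treatment without progression: adverse events, intercurrent illness and patient decision (7.3), and prolonged drug holds (8.2: "Patients may have either drug held for any reason for up to 21 days before discontinuing study treatment"). If the phone date is then used for censoring, every such patient adds unexamined time to the curve, including time on another therapy.

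The error can only lengthen PFS. The trial has 25 evaluable Phase 2 patients and no control arm to share the bias, and its median is compared with an outside figure of 6 weeks. The protocol does use an assessment-based date in Phase 1, where certain patients who stop early are censored at their last DLT assessment (4.1). The Phase 2 primary endpoint has no equivalent.

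**Working it through.** **The plan's own figure.** Section 4.1 claims 90% power with n = 25 for medians of 6 versus 18 weeks, two-sided alpha 0.05, and names no test. Assuming exponential PFS, a one-sample test of the 6-week proportion has p0 = 0.50 and p1 = 0.5^(6/18) = 0.794.

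Power = Φ[(√25 × 0.294 − 1.96 × 0.5) / √(0.794 × 0.206)] = 88.6%.

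That is close to the stated 90%. Other plausible tests give 70.5% to 99.98%. The censoring rule enters none of these formulas, so the power statement does not bear on this point.

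**One patient.** Suppose a patient stops at week 5 for toxicity, before the first scan at week 6, and stays alive. With calls every 13 weeks after stopping, the contacts fall at weeks 18, 31, 44 and 57. At the last of these the literal rule records 57 progression-free weeks; last-scan censoring records day 1. An End of Study scan within 28 days would support at most week 9.

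**Hand approximation for the group.** Assumptions: true median 6 weeks, exponential times, and a share q stopping before true progression. The probability that neither progression nor stopping has occurred by week 18 is e = 0.5^[3/(1 − q)]. The literal rule counts these patients plus everyone already stopped:

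S(18) = e + q(1 − e)

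- q = 0.10: 0.099 + 0.090 = 18.9%
- q = 0.20: 0.074 + 0.185 = 25.9%
- q = 0.30: 0.051 + 0.285 = 33.6%

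The truth is 0.5^3 = 12.5%. This ignores deaths among stopped patients (which lower S) and progression missed between the last scan and stopping (which raises it).

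Solving S(t) = 0.5 gives t = 6(1 − q) × log2[(1 − q)/(0.5 − q)] = 6.3, 6.8 and 7.6 weeks. That shift looks modest, but progression is recorded only at scans. A curve still just above 50% after the week-6 scan can therefore yield a median of 12.

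**Simulation.** Settings: n = 25; scans every 6, 8, then 12 weeks as in 4.1; calls every 13 weeks in year 1, then every 26; median post-progression survival 26–52 weeks; data cut at 52–104 weeks; 1,500–3,000 trials per setting. True median 6 weeks:

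| Quantity | 10% stop | 20% stop | 30% stop | Comparison |
|---|---|---|---|---|
| 18-week PFS, written rule | about 18% | 23–25% | 29–31% | truth 12.5% |
| Median ≥12 weeks, written rule | 48–51% | 52–59% | 61–66% | full scanning 41–46% |
| Median ≥12 weeks, last-scan censoring | 43–45% | 45–48% | 45–51% | full scanning 41–46% |
| Lower 95% limit above 6 weeks, written rule | 2.8–3.4% | 4.2–5.1% | 7.2–8.0% | full scanning 1.8–2.5% |

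A repeat run put the last row at 3.0–3.3%, 4.0–4.7% and 4.9–7.6%.

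With a true median of 12 weeks, the recorded median reaches the 18-week design target in 51–52%, 54–60% and 62–66% of trials, against 44–48% with full scanning.

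**Independent checks.** A large-sample calculation (true median 6 weeks; median survival 40 or 60 weeks) gave a literal-rule Kaplan–Meier median of 6.0 weeks at 10%, 8.6–12.0 at 20% and 12.0 at 30%. Last-scan censoring gave 6.0 throughout. Each stopped patient gained about 30–34 weeks of counted time on average.

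Another simulation gave larger effects. There, 10–30% refers to stopping before true progression, and progression arising between scans is also lost if the patient stops before the next one. Eighteen-week PFS was 20–40% under the literal rule and 17–33% with last-scan censoring. The median reached 12 weeks in 51–85% and 48–70% of trials respectively, against 37–47% with full scanning.

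**If an End of Study scan exists.** With one scan 4 weeks after every stop, the bias in the median largely disappears (≥12 weeks in 34–43%, true median 6). Eighteen-week PFS is still about 16%, 19% and 22–23%.

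**The case against.** **The term has another reading.** Section 11 repeatedly uses follow-up to mean tumour assessment, and in 4.1 the censoring sentence is followed by the visit and CT schedule. On that reading the authors may have meant the last scan. This stands as evidence of ambiguity. It does not supply a rule, and the section devoted to follow-up (7.4) points the other way.

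**Scans after stopping are not excluded.** The CT schedule in 4.1 does not say that it ends with treatment, the Schedule of Events is not visible, and sections 10, 12 and 13.2 are absent from the supplied text. So the claim that this is the only rule holds for the supplied text. Even with an End of Study scan, the censoring date as written is unchanged.

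**The stopping rates are assumed.** This is correct. Thirty percent stopping before progression with a 6-week median implies about 33% stopped by week 8, above the 25% DLT target in Phase 1. Section 7.5 also allows some withdrawn patients to be replaced. The upper figures may be pessimistic.

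**The metrics are not decision rules, and the design case is little affected.** The plan has no 12-week threshold. At a true median of 18 weeks, a check found the median reaching 18 weeks in 92% of trials under the literal rule against 91% with last-scan censoring at 10% stopping, and in 95–96% against 91–92% at 30%. The harm is mainly that a weak or inactive regimen looks better than it is.

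**Conclusion.** The concern holds. As written, the primary endpoint has a censoring date not tied to assessment of the event, and taking it literally biases PFS upward with no control arm to offset it. That phone dates would be used is a reading of the text, not an explicit instruction.

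The size rests on the assumed 10–30% stopping range and on exponential times. At 10% the effect is small. At 20–30% the median can be recorded one scan later than it should be, and 18-week PFS can be about twice the true value or more. An End of Study scan would remove most of the bias in the median but not all of it at 18 weeks. This should be fixed before analysis, because choosing the date afterwards would depend on the data.

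**What to change.** Replace the censoring sentence in 4.1 and repeat it in 11.6 and 13.3.1:

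*Patients alive without documented progression are censored at their last adequate tumour assessment before any new anti-cancer therapy (day 1 if none).*

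Keep death from any cause as an event in the primary analysis, as the protocol defines it. Add two sensitivity analyses:

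- (a) deaths after two or more missed assessments are censored at the last scan;
- (b) symptomatic deterioration and new anti-cancer therapy count as events.

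The cost is one sentence in three places and two extra analyses, with no new visits, scans or patients. Reported PFS may be slightly shorter.

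The fix is partial. A stopped patient who later dies unscanned is still an event at death, so 18-week PFS stays at 15–26% in the main simulation (17–33% in the harsher one) against a true 12.5%, and would be higher if stopping is related to prognosis. Sensitivity analysis (a) errs the other way (median ≥12 weeks in 22–36%), so it should not be primary.

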#### **4.2 Dose Limiting Toxicities for Phase I**

All patients who receive at least one dose of both study drugs will be evaluable for toxicity.

In order for a patient to be evaluable for DLT assessments, the patient must either incur a DLT during the DLT evaluation period or have received at least 80% of the planned doses of Sirolimus and Turalio®. Patients who do not fulfill one of these criteria should be considered non-evaluable for DLT assessment purposes, and be replaced.

A DLT is defined as an AE assessed as being possibly, probably, or definitely related to study drug administration that is:

- Not due to the underlying malignancy;
- Has no clear evidence of an alternative etiology; and
- Meets one of the following CTCAE v.4.03 criteria during the first 56 days of Turalio® and Sirolimus administration:
  - Any Grade  $\geq 4$  hematologic toxicity except grade 4 lymphopenia
  - Grade 3 neutropenia with fever
  - Grade 3 thrombocytopenia with clinically significant bleeding
  - Any circumstance that results in dose reduction.
  - Any Grade  $\geq 3$  non-hematologic toxicity except:
    - Nausea, vomiting, and/or diarrhea of Grade 3 severity that resolves within 3 days with optimal prophylaxis and/or treatment.
    - Grade 3 fatigue that resolves to Grade  $\leq 2$  within 2 days.
    - Grade  $\geq 3$  alkaline phosphatase that is related to underlying malignancy (eg, bone metastasis)
    - For hypercholesterolemia, hypertriglyceridemia, and hyperglycemia if unresolved after appropriate treatment with standard of care.

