**Columbia University Medical Center**  
**Herbert Irving Comprehensive Cancer Center**  
**Version Date: 04/21/2021**

these events, we impose a minimum of 2 weeks of observation between consecutive patients. Patients who discontinue treatment because of progression of disease or death unrelated to treatment without experiencing a DLT will be censored at the time of their last DLT assessment and included up to the point of their last assessment. If the last assessment occurs prior to the 4 week DLT assessment, that is, prior to the end of the first cycle of treatment, the patient will be replenished. To the contrary, if the last assessment occurs 4 weeks or after, that is, after the end of the first cycle of treatment assessment and the patient received at least 80% of the planned doses of Sirolimus and Turalio® the patient will not be replenished. Upon Daiichi Sankyo's request, CUMC will provide updates for the total number of patients enrolled in the study.

[figure not shown]
The TITE-CRM with an empiric dose-toxicity model, a linear weight function and a normal prior distribution on the parameter with mean 0 and variance of 1.34 is used. The dose-toxicity model is calibrated such that the method will eventually select a dose that yields between 18% and 32% DLT (31, 32). The design does not allow for dose skipping or dose escalation immediately after a DLT is observed (33). The performance of the TITE-CRM is assessed under five potential scenarios with scenarios 3 and 4 being the most likely. The operating characteristics of our design given 2000 simulations are displayed in Table 2. With 18 patients, the design selects the correct MTD with probabilities over 53% for all scenarios. The scenarios were selected to have neighboring doses with DLT rates within 15% of the MTD rate. If the neighboring doses have DLT rates significantly different from the target of 25%, the probability of correct selection will be improved. Likewise, if the neighboring doses have DLT rates very similar to the target rate, the probability of correct selection will worsen.

| Doses of Sirolimus
Doses of Turalio®
Dose Level | 2mg
600mg
1 | 2mg
800mg
2 | 2mg
1000mg
3 | 4mg
1000mg
4 | 6mg
1000mg
5 |
|---|-------------------|-------------------|--------------------|--------------------|--------------------|
| Scenario 1  |                   |                   |                    |                    |                    |

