### **8. DOSING DELAYS/DOSE MODIFICATIONS**

#### **8.1 Phase 1 Dose Modification**

All patients may have dose modifications at any time. During Cycle 1 in the phase 1 portion, however, the DLT must be recorded for safety purposes prior to dose reduction. Patients may have drug held for any reason for up to 14 days before discontinuing study treatment. Refer to Tables 4 - 7 below for specific dose modification instructions.

Patients will undergo therapeutic monitoring with trough levels of Sirolimus on day 2 of cycle 1 before receiving daily dose of Sirolimus on day 2 (+2 day window), day 8, day 15, and day 22 of Cycle 1, on day 1 of each subsequent cycle, unless clinically indicated, and during the End-of-Study visit. Trough levels may be measured at other time points as clinically indicated. As levels  $>18.0\mu\text{g}/\text{L}$  are more likely to be associated with an adverse events, dosing of Sirolimus will be held and/or reduced in the case of trough levels  $>18.0\mu\text{g}/\text{L}$  as indicated in the dose modification table (Table 4). Deviation of this dose modification can be done at the discretion of the treating investigator in discussion with the study principal investigator.

| Sirolimus Monitoring and Dose Modification |   |
|---|---|

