8.1.1 Dose Modification for Hepatotoxicity, Nausea/Emesis, and Hyperglycemia

8.1.1.1 **Hepatotoxicity** – Turalio® and Sirolimus should be discontinued if hepatotoxicity is observed as detailed in Table 5.

Reductions or interruptions of the Turalio® dose for toxicity may take place at any time during the study according to the guidelines in [Tables 5 and 6](#). Dose reduction/interruption guidelines for hematologic and nonhematologic treatment-related TEAEs are based on severity. Dose interruptions can be implemented at the discretion of the treating Investigator to manage intolerable or clinically significant toxicity. If a dose interruption is required, study assessments should be performed as scheduled, irrespective of the study drug delay, with the exception of PK assessments, which should be deferred until treatment is resumed. Interruptions due to toxicity lasting  $>14$  d require treatment discontinuation unless the medical monitor approves continuation.

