**Table 9: Recommended Turalio® and Sirolimus Dose Modifications**

Dose interruptions for Grade 2 non-hematologic toxicity for up to 1 week can be implemented at the discretion of the treating physician to manage intolerable or clinically significant toxicity. No dose reduction is required when resuming treatment.

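### The Phase 1 DLT definition counts related toxicity that lowers the dose but has no criterion for related toxicity that ends treatment, so some treatment-ending events can be scored as no DLT or replaced

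*Combined protocol and SAP*

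**What the plan says.** **DLT criteria (Section 4.2).** A related event within 56 days is a DLT if it meets a listed grade threshold (broadly Grade 4 hematologic or Grade 3 non-hematologic, with exceptions) or falls under "Any circumstance that results in dose reduction". Grade 3 nausea, vomiting or diarrhea that resolves within 3 days is exempt from the grade criterion, as is Grade 3 fatigue that settles within 2 days. Permanent discontinuation is not on the list.

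**Evaluability (Section 4.2).** A patient "must either incur a DLT during the DLT evaluation period or have received at least 80% of the planned doses" of both drugs; anyone else "should be considered non-evaluable for DLT assessment purposes, and be replaced".

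**Dose modification (Section 8.1).** Reducing and stopping are separate actions in Tables 4, 7 and 9. Table 4 labels only the reduction a DLT. The general hold rule is "Patients may have drug held for any reason for up to 14 days before discontinuing study treatment". Section 8.1.1.1 adds that longer interruptions for toxicity "require treatment discontinuation unless the medical monitor approves continuation".

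**Partial follow-up (Section 4.1).** "Patients who discontinue treatment because of progression of disease or death unrelated to treatment without experiencing a DLT will be censored". The sentence does not mention patients who stop because of toxicity.

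**Replacement (Section 7.5).** Discretionary replacement is described for withdrawals for reasons other than toxicity or clinically significant progression.

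**The concern.** A toxicity that forces a patient off treatment is at least as dose-limiting as one managed by stepping down a level. If the second is counted and the first is not, the DLT scale is out of order for those events. The TITE-CRM then receives either a zero or no patient at all. Either way the estimate at that dose moves down, and selection can move up.

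At stake is the recommended Phase 2 dose. Dose level 3 is given to every Phase 2 patient, and safety at that dose is a Phase 2 primary objective. Section 13.3.1 still requires the DLT proportion at each level and the final model estimates, so the question remains live although Phase 1 enrolment is complete.

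**Working it through.** **1. Which treatment-ending events escape the list?**

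| Event (related, within 56 days) | Action in Section 8.1 | Status under Section 4.2 |
|---|---|---|
| Grade 3 nausea/vomiting, delay under 48 h | Table 7: restart at a lower dose | DLT, by reduction |
| Same, delay 48 h or more, resolved within 3 days | Table 7: discontinue | Exempt by grade, no reduction: no DLT |
| Exempt Grade 3 event (e.g. brief fatigue), level 2 or above | Table 9: reduce one level | DLT, by reduction |
| Same event at level 1 | Table 9: discontinue both drugs | No DLT |
| Lower-grade toxicity held beyond 14 days | Discontinue, unless the medical monitor approves continuation | No criterion met |

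The first two pairs show the inversion inside the protocol's own tables.

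**2. What happens to those patients?** In a 56-day window, 80% is 0.80 × 56 = 44.8 days. Missing more than 14 days leaves less than 42/56 = 75%. If planned doses are counted over the whole window, such a patient is non-evaluable and replaced under 4.2. If the 80% is already met when treatment stops, or is counted over Cycle 1 only, the patient can stay in as a non-DLT.

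**3. Reproducing the plan's figure.** Model: DLT probability at level k is s_k^exp(b), with b ~ N(0, 1.34), evaluated at the posterior mean of b. The skeleton s is built from the stated 18–32% interval around 25%. The prior MTD level is not stated. The Figure 4 description gives 0/2, 0/3, 1/10 and 2/3 at levels 2 to 5. Prior MTD at level 2 (skeleton 0.124, 0.250, 0.398, 0.542, 0.666) gives 18.6% (6.0%, 36.6%) at level 4, against the stated 18.6% (6%, 37%). Simulated correct selection is 74.8, 55.2, 54.3, 53.4 and 68.2%, against Table 2's 74, 55, 53, 53 and 66%. Table 2 is not in error, but it takes every dose-limiting event as counted.

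**4. Illustration with assumed counts.** The documents give no per-dose data. Assume 18 fully followed patients: 0/3 at level 2, 2/11 at level 3, 2/4 at level 4. Add replaced patients back at level 3 as DLTs, using the skeleton from step 3:

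| Restored | Level 3 data | Level 3 estimate | Distance from 25% |
|---|---|---|---|
| 0 | 2/11 | 21.7% | 3.3 points |
| 1 | 3/12 | 26.0% | 1.0 |
| 2 | 4/13 | 29.8% | 4.8 |
| 3 | 5/14 | 33.2% | 8.2 |

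At three, level 2 is estimated at 19.1%, which is 5.9 points from target and so nearer than level 3. With prior MTD at level 4 the corresponding values are 31.5% (6.5 points) and 17.6% (7.4 points), and level 3 is kept. With one or two restored, level 3 is selected under prior MTD levels 1 to 5. These results are for replaced patients added back. A patient already among the 11 and rescored moves the rate further, because the denominator does not grow (crude 3/11 = 27.3% against 3/12 = 25.0%), so they do not carry over to rescoring.

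**5. Effect on selection, by assumed share missed.** Let f be the share of true dose-limiting events that escape the list; 10–30% is an assumption. The observed rate is p(1−f) if they are scored as no DLT, and p(1−f)/(1−pf) if replaced. At p = 25% and f = 20% these are 20.0% and 0.20/0.95 = 21.1%. In Table 2's scenario 3 (skeleton from step 3), the simulated chance of selecting above the true MTD is:

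| f | Scored as no DLT | Replaced |
|---|---|---|
| 0 | 21% | 21% |
| 10% | 31% | 28% |
| 20% | 41% | 35% |
| 30% | 53% | 44% |

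**The case against.** The best defence is that the gap is narrow and may have had no effect. Related Grade 3 non-hematologic and Grade 4 hematologic events are mostly DLTs by grade whatever happens to the dose. The 14-day stop is not automatic, since the medical monitor can approve continuation, and the text before Table 9 speaks of three weeks with a clinical-benefit exception. For Grade 2 non-hematologic toxicity, the text after Table 9 foresees holds of up to one week and adds "No dose reduction is required when resuming treatment". The lower-grade route therefore rests on the general hold sentences alone. Section 7.5 points against replacing patients withdrawn for toxicity. All of this stands, and it limits the point. It does not remove the Table 7 case, and 7.5 conflicts with 4.2 without overriding it. The provision in 8.1 for weighing other toxicities when choosing the dose covers those outside the DLT window, not in-window events that miss the list.

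A reader might infer that liver injury is the event most exposed, because 8.1.1.1 calls for discontinuation. The documents do not support that. Table 5, which governs it, is not in the text available for review; the same section also refers to reductions and interruptions; Table 6 allows Turalio to be started again after recovery; and related Grade 3 or higher hepatic events are generally DLTs by grade.

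It is also fair that redefining the DLT once the data are known would be a post hoc change of endpoint. That argues for a sensitivity analysis, not a replacement estimate.

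**Conclusion.** The point holds as a limited gap in the DLT definition. Followed as written, the plan can score some treatment-ending related toxicity as no DLT, or replace the patient. Either can only lower the DLT estimate. The affected events are those below or exempt from the grade thresholds, with Grade 3 nausea or vomiting delayed 48 to 72 hours the clearest.

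The size is unknown. A reader might infer that the recommended dose is biased or that level 3 is wrong; the documents show only that the rule permits bias, and none records even one such patient. In the illustration, one or two restored patients raise the level 3 estimate to 26.0% or 29.8% without changing the selection. Three raise it to 33.2%, and whether level 3 is then kept depends on the skeleton. Those figures rest on assumed counts, complete follow-up and an inferred prior MTD level.

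**What to change.** 1. List every treated Phase 1 patient, including those replaced, who permanently stopped either drug within 56 days for an adverse event at least possibly related to study drug.
2. Re-run the TITE-CRM with these patients counted as DLTs. Report it as a labelled sensitivity analysis beside the estimates that Section 13.3.1 requires, and leave the planned estimates unchanged.
3. State whether dose level 3 is still the selected level.
4. Reconcile Sections 4.1, 4.2, 7.5 and the Section 8.1 tables on how a toxicity-driven discontinuation is scored and whether such a patient may be replaced. No dose or stopping rule is proposed here.

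The cost is a review of 18 evaluable patients plus any replaced, one model run on data already held, and a wording clarification. The downside is that the reported DLT rate at dose level 3 may be less favourable.
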